3.2 Statistical Analysis Issues

A retention rate of 95% is targeted. Based on previous MTN trials, minimal missing data is expected. If missing data rates are higher than anticipated (over 10%), sensitivity analyses will be conducted to assess the impact of missing data on trial inference. If missing data rates are over 10 and assuming missing data are ignorable, we will use multiple imputation based on all available baseline predictors and available trial outcomes. Otherwise, we will complete analyses using available data.

For primary safety analysis, safety endpoints will be classified by the product used at that particular period, starting from date of enrollment or most recent product switch visit. If a participant did not receive a particular product then that participant-period will be excluded from the analysis. Due to COVID-19, some participants have received multiple products in advance or have received product through mail. The actual product switch visit date for the corresponding product will be used as the start of the product use period instead of the date participants received the product. A safety endpoint will be considered to have occurred during a specific product use period if the onset date of the AE is on or after start of the product use period (enrollment or switch visit date) and before the start of the next product use period (switch visit date or end of study).

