6.2 Treatment Exposure

The number and percentage of participants who received each of the three study products, along with the number and percentage of participants who completed the corresponding product use end visit (PUEV) will be displayed in a table overall and by site, and in a table overall and by randomized sequence. In addition, the number and percentage of participants who received all three study products and completed all three PUEV will also be displayed.

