9. PRIMARY SAFETY ANALYSES

All participants enrolled and administered a study product will be assessed for safety.

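### SAP 3.2 keeps a participant-period in the primary safety analysis if the product was received, even if it was never used, although COVID-19 supply changes separated receipt from use

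*SAP*

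**What the plan says.** SAP 3.2 sets four rules or facts for the primary safety analysis:

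- **Exclusion.** "If a participant did not receive a particular product then that participant-period will be excluded from the analysis". No other ground for excluding a participant-period is stated.
- **Supply.** "Due to COVID-19, some participants have received multiple products in advance or have received product through mail".
- **Start of period.** "The actual product switch visit date for the corresponding product will be used as the start of the product use period", in place of the date of receipt.
- **AE window.** An AE belongs to a period if its onset is "on or after start of the product use period (enrollment or switch visit date) and before the start of the next product use period". If no further switch visit takes place, the window stays open to the end of the study.

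The same section also says that "safety endpoints will be classified by the product used at that particular period, starting from date of enrollment or most recent product switch visit".

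Other sections use different tests. SAP 3.1 defines the safety set by receipt of at least one product. SAP 9 says "All participants enrolled and administered a study product will be assessed for safety". Protocol 10.7.2 bases the primary safety analysis on visits at which the participant was exposed to product. SAP 6.2 will tabulate "The number and percentage of participants who received each of the three study products" together with completion of the matching product use end visit (PUEV). It has no count of participants who started each product.

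**The concern.** As the protocol was written, receipt, switch visit and first use fell on the same day. Product is dispensed at Enrollment, Visit 4 and Visit 6 (protocol 6.5), and the first dose of each product is taken in the clinic (protocol 6.2 and Tables 5 and 7). Receipt was then a safe stand-in for exposure.

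The SAP reports that this link broke during COVID-19. It moved the start of the period to the switch visit but left receipt as the inclusion test. Two consequences follow from the literal text:

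1. **Denominator.** Take a participant who holds products 2 and 3 and leaves before the third switch visit. Product 3 was received, so the period is not excluded. It has no start date, so no AE can be assigned to it. It adds a certain non-event to that product's percentage.
2. **Attribution.** If a product supplied ahead is used before or without its switch visit, the previous product's window is still open and takes the AE.

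Primary safety is reported as a percentage per product with an exact interval (SAP 9.1), and the between-product safety models in SAP 10 would use the same participant-periods. The first effect can only lower a product's rate. The second moves events between products.

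**Working it through.** **Inputs.** Planning n = 200 (SAP 2.5, 5% dropout from about 210). Clopper-Pearson intervals (SAP 9.1); that section gives no level, so two-sided 95% is assumed, as in SAP Table 2. The number k who received a product and never started it is not in the documents; it is assumed to be 0 to 40 of 200. The number of misassigned events is also not given; one is used for illustration.

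**Step 1: the plan's own figures.** SAP Table 3 was checked with (1−p)^200 for zero events and exact binomial tails for at least 1, 5 and 10 events.

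| True rate | Recomputed | SAP Table 3 |
|---|---|---|
| 1% | 13.4%, 86.6%, 5.2%, 0.0% | 13%, 87%, 5%, 0% |
| 2% | 1.8%, 98.2%, 37.1%, 0.75% | 2%, 98%, 37%, 1% |
| 5% | 0.0%, 100%, 97.4%, 54.5% | 0%, 100%, 97%, 55% |

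The 0.1% and 0.5% rows also agree. The table is correct, and this point does not affect it.

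**Step 2: dilution.** With x events among 200 − k who started, the receipt-based rate is x/200 and the rate among starters is x/(200 − k). Their ratio is (200 − k)/200. With zero events the upper limit is 1 − 0.025^(1/n).

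| k | Ratio | 4 events: among starters (receipt-based: 2.00%, 0.55 to 5.04) | 0 events: upper limit among starters (receipt-based: 1.83%) |
|---|---|---|---|
| 5 | 0.975 | 2.05% (0.56 to 5.17) | 1.87% |
| 10 | 0.95 | 2.11% (0.58 to 5.30) | 1.92% |
| 20 | 0.90 | 2.22% (0.61 to 5.59) | 2.03% |
| 40 | 0.80 | 2.50% (0.69 to 6.28) | 2.28% |

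**Step 3: how large k could be.** k consists mainly of people supplied ahead who left before that product's switch visit. At the targeted 95% retention, total loss is about 210 × 0.05 = 10.5. So k = 10 for a single product already equals the whole planned loss, and k = 20 is about twice it. The six sequences also place each product in each period equally often. If 10 people left with one unopened product each, the expected number per product is 10/3, or about 3. COVID-19 may have worsened retention, but no figure is given.

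**Step 4: attribution.** One event moved changes a rate by 1/200 = 0.5 percentage points. Two products each truly at 4/200 (2.0%) would be reported as 3/200 (1.5%) and 5/200 (2.5%). If 10 people used a product with no switch visit and the true rate were 2%, the expected number of misassigned events is 10 × 0.02 = 0.2.

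**The case against.** The strongest reply is that the quoted sentence is an exclusion, not a statement that receipt is sufficient. SAP 3.2 classifies endpoints by the product used and counts from the switch visit, so one can argue that without a switch visit there is no period to include. SAP 9 and protocol 10.7.2 both point to use. That is a sensible reading and may be what the authors intend. But the SAP does not say it: its only stated exclusion is non-receipt, and SAP 3.1 also relies on receipt. Two programmers could reach different denominators from the same text.

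It is also fair that a switch visit held remotely still supplies a start date, and that a gap between the received and PUEV counts in SAP 6.2 would give a warning. That gap, however, mixes people who never started with people who started and missed the PUEV.

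A reader might infer more than the documents support:

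- **That AEs have been credited to the wrong product.** No document reports anyone using a product before or without its switch visit. The text only leaves such a case to the previous product.
- **That one misassigned event would change a rate by 25 to 50%.** This is arithmetically true of 4 or 2 events, but it presumes a whole misassigned event. Step 4 shows that well under one would be expected even if 10 people were affected.
- **That the intervals are seriously too narrow.** At k = 10 the upper limits differ by 0.09 percentage points with no events and 0.26 with four.

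**Conclusion.** The point holds as a gap in a primary safety rule, with an effect that is probably small. Taken literally, SAP 3.2 leaves received but unused products in the denominator, which conflicts with the exposure basis of protocol 10.7.2 and the administration basis of SAP 9. The bias from dilution runs one way, towards a lower event rate. At an assumed k = 10 of 200 it is 5% in relative terms.

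The size rests on assumed counts, because the documents do not say how many participants were supplied ahead, how many of them never started, or whether anyone used a product outside its visit window. The documents do not show that the safety results would be materially wrong. They show that the rule is incomplete at the place where the SAP itself reports the departure from the protocol's dispensing scheme, and that closing the gap costs little.

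**What to change.** 1. **SAP 3.2, and SAP 3.1 for the safety set only.** Include a participant-period for a product only if the participant used at least one dose of it. Evidence is in-clinic application at the enrollment or switch visit, or use reported by SMS/IM or CASI. A switch visit alone should not qualify, since a remote visit with no use would leave the dilution in place.
2. **Period start.** Keep the switch visit date. Where use is reported before or without a switch visit, assign AEs to that product from the start of the first weekly report showing use. The documents show no field for an exact first-use date, so the week is the finest available unit.
3. **SAP 6.2.** Keep the received count and add a started count for each product. The difference shows how many participant-periods the rule affects; replacing the received count would hide it.
4. **No change to the per-protocol acceptability and adherence set.** It already requires all three PUEVs.

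The cost is a few sentences of SAP text and some programming on data already planned: visit records, weekly SMS/IM reports and CASI (protocol 7.4.1 and 7.8). The downsides are slightly smaller denominators and approximate start dates in the few cases without a switch visit.

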### **8.3.3 Adverse Event Relationship to Study Product**

Relatedness is an assessment made by a study clinician of whether or not the event is related to the study agent. Degrees of relatedness will be categorized according to current DAIDS-approved guidelines. Per the Manual for Expedited Reporting of Adverse Events to DAIDS (Version 2.0, January 2010), the relationship categories that will be used for this study are:

- *Related*: There is a reasonable possibility that the AE may be related to the study agent(s)
- *Not Related*: There is not a reasonable possibility that the AE is related to the study agent(s)

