## **10.2 Study Endpoints**

Consistent with the primary study objective to evaluate the acceptability and tolerability of a placebo insert, a placebo douche, and a placebo suppository when applied rectally and used prior to RAI, the following endpoints will be assessed on a scale of 1 to 10 for each study product:

- Participant self-report of likelihood of product use if shown to be effective

Consistent with the primary study objective to evaluate adherence to a placebo insert, a placebo douche, and a placebo suppository when applied rectally and used prior to RAI over a 4-week-long period, the following endpoints will be assessed for each study product:

- Per participant report, percentage of occasions when study product was used as instructed (per protocol)

Consistent with the primary study objective to evaluate the safety of a placebo insert, a placebo douche, and a placebo suppository when applied rectally and used prior to RAI, the following endpoints will be assessed for each study product:

- Grade 2 or higher related AEs as defined by the Division of AIDS Table for Grading the Severity of Adult and Pediatric Adverse Events, Corrected Version 2.1, July 2017, and/or Addenda 1, 2 and 3 (Female Genital [Dated November 2007], Male Genital [Dated November 2007] and Rectal [Clarification Dated May 2012] Grading Tables for Use in Microbicide Studies)

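### The SAP starts each product's safety window on the switch-visit date and not at the first dose, so a related adverse event can be counted to a product not yet used

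*SAP*

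**What the plan says.** Protocol section 10.2 defines safety per product: "the following endpoints will be assessed for each study product", the endpoint being Grade 2 or higher related adverse events. SAP section 9.1 tabulates it by product with Clopper-Pearson intervals.

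SAP section 3.2 supplies the attribution rule. In principle, "safety endpoints will be classified by the product used at that particular period". In practice an event belongs to a product "if the onset date of the AE is on or after start of the product use period (enrollment or switch visit date"). That sets the lower limit, with the switch day included. The upper limit of the window reads "and before the start of the next product use period (switch visit date or end of study"). The same section notes that, because of COVID-19, "some participants have received multiple products in advance or have received product through mail". For those participants, "The actual product switch visit date for the corresponding product will be used as the start of the product use period", in place of the date of receipt. The date of first dose does not appear in the rule.

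Protocol section 6.2 has participants take the first dose of each product in the clinic. Table 7 places adverse event recording and the first application of the new product at the same visit (Visits 4 and 6). Protocol section 10.7.2 builds the primary safety analysis on visits at which the participant was exposed to the product, and leaves the washout to optional secondary analyses.

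**The concern.** A per-product rate of related events should count only events that begin after that product has been used. The SAP's boundary is a calendar day, and that day contains both time before and time after the first dose of the new product. Where product was mailed or supplied ahead, the first dose need not fall on the switch-visit date at all. In either case the rule can place an event on a product to which the participant has not yet been exposed, which does not fit the exposure basis in protocol section 10.7.2.

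Every participant is meant to use all three products, so the per-product answer rests on this assignment. The numbers will be small, and protocol section 2.2.1 states that the insert has no human data from rectal use. The difference between zero and one event on a product will be read closely.

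**Working it through.** **Inputs.** n = 200 and event rates of 1% and 2% (SAP section 2.5, Table 3). Switch visits at Day 35 and Day 70 (protocol section 6.5). Washout of about 7 days between product use end visit and switch visit, and final visit about 7 days after Visit 7 (sections 7.4.2 and 7.4.3). Six sequences A to F (Table 1). The documents give no misassignment rate, so the fraction *f* below is an assumption shown over a range.

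**1. The plan's own figures.** P(0 events) = (1 − p)^200 gives 0.134 at 1% (stated 13%) and 0.018 at 2% (stated 2%). The binomial tail gives P(≥5) = 0.371 at 2% (stated 37%) and P(≥10) = 0.545 at 5% (stated 55%). All 20 cells of SAP Table 3 reproduce. Expected counts are 200 × 0.01 = 2 and 200 × 0.02 = 4.

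**2. The rule applied case by case.**

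| Onset of event | Counted to | Exposed to that product? |
|---|---|---|
| During use or washout, before the switch day | Previous product | Yes |
| Switch day, before the clinic dose | New product | No |
| Switch day, after the clinic dose | New product | Yes |
| After the switch visit, before a later first dose | New product | No |
| After use of the next product ahead of its switch visit, if that happened | Previous product | Yes, but also to the next product, which is not credited |

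**3. Size of the switch-day window.** The nominal windows are days 0–34, 35–69 and 70–104, each 35 days. One day is 1/35 = 2.9%. Only the pre-dose part is exposed, which lowers this. Against that, adverse events are recorded at that visit, so onset dates may cluster there.

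**4. Expected shift in rates.** Each ordered pair of products occurs in 2 of the 6 sequences. Suppose a fraction *f* of period 1 and period 2 events moves to the next product. A product with true count T then loses (2/3)·f·T and gains (1/3)·f·(sum of the other two counts). Take illustrative true counts of 10, 2 and 2 per 200 (5%, 1%, 1%). The first product becomes 10 − 6.667f + 1.333f = 10 − 5.333f. Each of the others becomes 2 − 1.333f + 4f = 2 + 2.667f.

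| f | First product | Each other product |
|---|---|---|
| 1/35 | 4.92% | 1.04% |
| 5% | 4.87% | 1.07% |
| 10% | 4.73% | 1.13% |
| 20% | 4.47% | 1.27% |

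The rates are drawn towards each other, and no product is singled out by the design.

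**5. Effect of one event.** Exact 95% intervals at n = 200:

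| Events | Rate | 95% CI |
|---|---|---|
| 0 | 0% | 0 to 1.83% |
| 1 | 0.5% | 0.01 to 2.75% |
| 2 | 1.0% | 0.12 to 3.57% |
| 3 | 1.5% | 0.31 to 4.32% |
| 4 | 2.0% | 0.55 to 5.04% |

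**The case against.** The best defence is that the rule is objective, prespecified and mostly right. It uses onset date, not date of discovery, so an event that began earlier but is first reported at the switch visit stays with the previous product. A rectal examination is required at each product use end visit, about a week earlier, and its findings also fall to the previous product. The SAP saw the COVID-19 supply problem and chose the switch visit over the date of receipt. The adverse event listing in SAP section 9.2 shows the product period, so boundary cases can be inspected. The goal is estimation, and between-product models are exploratory. All of this stands, and it limits the size of the problem. It does not close the two gaps in step 2.

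A reader might infer four stronger things that the documents do not support:

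- **That any event present before the new product's first dose is misassigned.** On the in-clinic schedule, only onsets on the switch day itself and before the dose are exposed.
- **That late effects of the previous product are a real source of error.** Such an event would have to start after a washout week already credited to that product, and nothing in the documents suggests such a delay.
- **That advance supply led to early use.** The SAP speaks of receipt only.
- **That no product-level causal assessment exists.** Protocol section 8.3.3 phrases the category as "There is a reasonable possibility that the AE may be related to the study agent(s") but the definition in the singular: "Relatedness is an assessment made by a study clinician of whether or not the event is related to the study agent". Section 9.4 asks for consultation on the particular product in use. The adverse event form is not among the documents, so product-level recording is unspecified, not shown to be absent.

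Nor does it follow that clinician-named attribution should become the primary rule. The trial is open label, and the safety review team includes representatives of the insert's developer (protocol sections 2.2.1 and 8.1). Replacing a date rule with unblinded judgement could introduce more bias than it removes.

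**Conclusion.** The gap is real and small. As written, SAP section 3.2 can count a Grade 2 or higher related event to a product not yet used, either on the switch day before dosing or between the switch visit and a later first dose. The reverse error, an event counted to the previous product after early use of the next one, depends on early use having occurred.

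If only the switch day matters and onsets are spread evenly, the illustrative rates move by less than 0.1 percentage point. A larger shift needs a larger *f*, for which there is no evidence either way. The case for acting rests on sparse counts. With 2 to 4 events per product, one misplaced event changes a rate by 0.5 percentage points and visibly moves its exact interval. The balanced sequences protect the expectation, not the realised count.

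A neighbouring inconsistency belongs to the same text. SAP section 3.2 runs each window through the washout to the next switch visit, so washout events enter the primary safety analysis, whereas protocol section 10.7.2 leaves the washout to secondary analyses.

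**What to change.** Amend SAP section 3.2 as follows.

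- Keep the date-based rule, but for periods 2 and 3 set the boundary at the first dose of the new product. Take it from the clinic application record, or from reported first use where the product was not first applied in clinic.
- Assign events with onset before that dose to the previous product. For onsets on the day of the first dose, record whether they came before or after it, since dates alone cannot order them.
- Fall back on the switch-visit date only when the first-dose date is unknown.
- Report the present switch-visit-date assignment as a sensitivity analysis. If the adverse event form already records the implicated product, report assignment by that product as a further sensitivity analysis, not as the primary rule.
- Reconcile the treatment of the washout with protocol section 10.7.2. If washout events leave the primary analysis, pre-dose switch-day onsets should leave with them.

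The cost is a few sentences in the SAP, a lookup of first-dose dates, and a before-or-after check for the few events that fall on a boundary day. The drawback is that first-dose dates outside the clinic may rest on self-report.

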4. INTERIM ANALYSIS AND DATA MONITORING COMMITTEE

No interim statistical analysis was planned or performed for the MTN-035 study.

Two study monitoring committee (SMC) review were conducted for MTN-035 on October 10, 2019 and May 4, 2020.

5. GENERAL ANALYSIS METHODS

When use of descriptive statistics is required for the assessment or comparison of study product group characteristics, the following statistics will be reported: for categorical variables, the number and percent in each category; for continuous variables, the mean, median, standard deviation, quartiles, and range (minimum, maximum).

6. TRIAL PARTICIPANT DISPOSITION

6.1 Disposition of Participants

6.1.1 Screening and Enrollment

Dates of site activation, first enrollment, and last enrollment, as well as the number or participants screened, number and percentage of participants enrolled, and the screening-to-enrollment ratio will be displayed in a table overall and by site.

6.1.2 Retention

The number and percentage of participants who are expected, retained, missing, and lost-to-follow-up or terminated with respect to the visit will be displayed for each visit in a table overall and by site, and in a table overall and by randomized sequence.

Interim visits completed to make up for a missed visit will be included in both tables. If a missed visit is made up by completing an interim visit, then the missed visit will be considered as completed in the retention tables.

